11.4 Baseline characteristics

Demographic and baseline characteristics shall be tabulated and summarised for the study. The following characteristics will also be tabulated and summarised both per centre and per procedure type:

-Age

-BMI

- -Gender
- -Procedural ACT
- -Sheath size
- -Sheath size to femoral artery diameter ratio
- -Hypertension
- -Diabetes
- -Severe acute non-cardiac systemic disease, autoimmune disease or terminal illness
- -Bleeding Diatheses
- -Clinically significant peripheral vascular disease

Subgroup comparisons will be tested and the results of these tests will be summarised by their respective p-values. As the primary endpoint will be analysed per centre and per procedure type (among others), we will compare the above baseline characteristics between these subgroups as well, in order to further explore any possible confounders for the relationships between the primary endpoint and both the centre and the procedure type.

11.5 Variables

The study variables identified for comparisons/summaries are:

Primary Variables:

- i. Major device related vascular access site complication rate.
- ii. Serious Adverse Device Effect (SADE), Unanticipated Serious Adverse Device Effect (USADE) rate, as defined in the 'Clinical Investigation Definitions' (which is maintained in the Site File for each site).

Secondary Variables

- i. Safety: minor vascular access site complications related to the closure.
- ii. Adverse Device Effect (ADE), Serious Adverse Event (SAE) or Adverse Event (AE) rate, as defined in the 'Clinical Investigation Definitions'.

Performance: assessed by technical success rate for the PerQseal® closure device.

The potential influencing variables identified include:

- i. Patient age, gender, weight or Body Mass Index (BMI)
- ii. ACT
- iii. Co-existent diseases
- iv. Sheath size used
- v. Common Femoral Artery (CFA) diameter
- vi. Procedure to be performed

11.6 **Primary endpoint analysis**

The Safety of the PerQseal® closure device will be assessed by comparison of the proportion of PerQseal® closure device subjects with device related major vascular access site complication up to 1 months (P_{safety}) against a performance goal for safety (PG_{safety}). (The performance goal for safety for this study will be based on historical data extracted from literature for cut-down and suture closure.)

This will be achieved by testing for non-inferiority against a safety non-inferiority limit (N_{LS}), which is the predetermined PG_{safety} plus a non-inferiority margin delta. In order to claim non-inferiority against a safety driven PG_{safety} the upper bound of a one-sided (95%) confidence interval for the proportion of subjects with complications " P_{safety} " (using the exact method for estimating a Binomial proportion) must be shown to be less than the non-inferiority limit.

The PG_{safety} and non-inferiority margin delta have been derived from a Meta-analysis of major vascular access site complication rates for cut-down and suture closure from equivalent patient populations and sheath sizes of 12 - 24 F reported in the literature:

The proportion of complications is estimated to be 0.125 with a 95% Confidence Interval of 0.09 to 0.17. Given that the upper bound is 0.17 this justifies the use of 0.13 as valid PG_{safety} plus a non-inferiority margin of 0.04 yielding an overall non-inferiority limit (N_{LS}) of 0.17 for Safety.

The test for non-inferiority for safety will be based on a one-sided test (at the 0.025 significance level) for a binomial proportion with hypotheses:

 H_{0S} : $P_{safety} \ge N_{LS}$ versus H_{1S} : $P_{safety} < N_{LS}$

Where: P_{safety} is the actual proportion of subjects with device related major vascular access site complications within the analysis population (ITT and PP).

And: N_{LS} is the non-inferiority limit for proportion of expected major vascular access site complications associated with cut-down and suture closure.

Non-inferiority analysis will be done by using the study data to calculate a confidence interval for the population proportion with major vascular access site complications directly related to the device. Demonstrating non-inferiority for safety necessitates rejecting the null hypothesis (H_{0S}) in favour of the alternative hypothesis (H_{1S}), in this case based on the upper limit of a 95% confidence interval for a population proportion being less than the non-inferiority limit.

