9.3 Study population

Patients will not be excluded on the basis of age, race, concomitant therapy or co-existing disease. Each centre will continue to enrol eligible patients until a minimum combined Clinical Investigation population of 75 patients is achieved.

Patients with bilateral percutaneous access in the common femoral arteries where both arteries meet all eligibility criteria may, at the discretion of the investigator, both be closed with the PerQseal® closure device. If a PerQseal® is used on the contralateral femoral artery then this will be treated as an independent closure i.e. each limb will be counted as a separate closure only for the purposes of Performance Analysis.

Consented patients who receive contact with the PerQseal[®] closure device become an enrolled subject.

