10. SAMPLE SIZE

The sample size estimate outlined below is based on primary endpoint assessment only for the PerQseal® closure device.

The primary endpoint of safety will be assessed by comparison of the proportion of PerQseal® closure device closures with device related major vascular access site complications up to 1 months (P_{safety}) against a performance goal for safety (PG_{safety}) estimated from literature to be 12.5%.

The minimum sample size to demonstrate non-inferiority of safety against the literature based non-inferiority limit of 0.17 (refer to: Section 11.6 Primary Endpoint Analysis) with a one-sided significance level of 0.025 and study power of 90% is estimated to be 68 closures (assuming a 5% major vascular access site complication rate for the PerQseal® closure device). Refer to the independent statistical report for safety sample size in the CIP Appendix F: Independent Statistical Sample Size Report for Safety for details.

A one sided confidence interval is appropriate as the study is only interested in the upper bound of the major complication rate. Each complication will be analysed as a separate event.

Completion of 75 patients is recommended, this number of patients should be sufficient to demonstrate non-inferiority whilst allowing for approximately 10% dropout rate.

For Performance, in order to claim non-inferiority against technical success rate for 'perclose' or 'preclose' technique the lower bound or a (95%) confidence interval for PerQseal® technical success rate must be shown to be greater than the performance non inferiority limit. In order to achieve this, a minimum sample size of 44 closures is required to demonstrate non-inferiority in a single sample fixed one-sided significance level of 0.025 and power of 0.90 level. The secondary performance endpoint therefore does not drive sample size. The total planned sample size remains at 75 treated subjects.

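### SAP 11.6 gives two different levels for the primary safety rule (a one-sided 95% bound and a one-sided 0.025 test), and 7 events in 75 subjects passes one and fails the other

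*SAP*

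**What the plan says.** SAP 11.6 states the success criterion for the only primary hypothesis three times:

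- The claim criterion requires "the upper bound of a one-sided (95%) confidence interval for the proportion of subjects with complications" to lie below the non-inferiority limit of 0.17, with the bound found by "using the exact method for estimating a Binomial proportion".
- The formal hypotheses follow: "The test for non-inferiority for safety will be based on a one-sided test (at the 0.025 significance level) for a binomial proportion".
- The closing sentence ties rejection of the null to an interval again, "in this case based on the upper limit of a 95% confidence interval for a population proportion being less than the non-inferiority limit", without saying whether that interval is one-sided or two-sided.

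The sample-size text, in SAP 10 and in the protocol synopsis, is worded "with a one-sided significance level of 0.025 and study power of 90% is estimated to be 68 closures", assuming a 5% device rate. Both documents add: "A one sided confidence interval is appropriate as the study is only interested in the upper bound of the major complication rate". Neither gives a confidence level for that one-sided interval.

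**The concern.** A one-sided 95% upper bound falls below the limit exactly when a one-sided test at 0.05 rejects. A one-sided 0.025 test corresponds to a one-sided 97.5% bound, which is the upper limit of a two-sided 95% interval. The claim criterion and the formal test in SAP 11.6 are therefore different rules.

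Both are operative: one says when the claim may be made, the other defines the test. An analyst who programs the claim criterion literally follows the SAP, and so does one who programs the test. The study is single-arm and unblinded. If the disputed count occurs, the favourable reading could be chosen after the data are seen, with the SAP cited in support.

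**Working it through.** **Inputs.** Limit p0 = 0.17 and exact binomial method (SAP 11.6); assumed device rate p1 = 0.05, 90% power, one-sided 0.025, 68 closures, 75 planned (SAP 10). Counts below are subjects with at least one device-related major complication, the unit used in SAP 11.6.

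**The plan's figure of 68.** Arcsine formula: n = [(z(1−α) + z(0.90)) / h]², with h = 2(arcsin√0.17 − arcsin√0.05) = 2(0.4250 − 0.2255) = 0.399.

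- α = 0.025: [(1.960 + 1.282)/0.399]² = 66.02, so 67, close to the stated 68. Approximate power at 68 is 0.908.
- α = 0.05: 53.8, so 54.
- Exact binomial at 0.025: power first reaches 90% at n = 74; at n = 68 it is 0.876.
- Exact binomial at 0.05: power first reaches 90% at n = 59 and stays there from n = 67.

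So 68 fits 0.025 by the arcsine formula, but an exact criterion at 0.05 also lands at 67. The number alone does not settle the intended level; the stated alpha of 0.025 is the better guide.

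**Bounds.** The exact (Clopper–Pearson) upper bound for x events in n is the 1−α quantile of Beta(x+1, n−x). Type I error for a rule passing at x or fewer is P(X ≤ x | n, 0.17); power is P(X ≤ x | n, 0.05).

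| n | x | one-sided 95% bound | one-sided 97.5% bound | P(X ≤ x) at 0.17 | P(X ≤ x) at 0.05 |
|---|---|---|---|---|---|
| 75 | 6 | 0.1518 pass | 0.1660 pass | 0.0204 | 0.919 |
| 75 | 7 | 0.1682 pass | 0.1829 **fail** | 0.0460 | 0.966 |
| 75 | 8 | 0.1842 fail | 0.1994 fail | 0.0906 | 0.988 |
| 68 | 5 | 0.1484 pass | 0.1633 pass | 0.0180 | 0.876 |
| 68 | 6 | 0.1667 pass | 0.1822 **fail** | 0.0434 | 0.947 |

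At n = 75 the literal interval rule passes with up to 7 events and the 0.025 test with up to 6. The type I error ratio is 0.0460/0.0204, about 2.3.

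**Other sample sizes.** SAP 9.3 describes enrolment "until a minimum combined Clinical Investigation population of 75 patients is achieved", so the analysed number is not fixed. The largest passing counts are:

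| n | 0.025 rule | 0.05 rule |
|---|---|---|
| 60–65 | 4 | 5 |
| 66 | 5 | 5 |
| 67–73 | 5 | 6 |
| 74 | 6 | 6 |
| 75–80 | 6 | 7 |
| 81 | 7 | 7 |
| 82–88 | 7 | 8 |
| 89–90 | 8 | 9 |

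The rules agree only at 66, 74 and 81, and differ by one event at the other 28 of 31 sizes. The 60–90 range is chosen here for illustration.

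**Chance of the disputed count.**

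- n = 75, x = 7: 4.7% if the true rate is 5%, 15.4% if it is 10%.
- n = 68, x = 6: 7.1% and 15.9%.

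The 10% rate is an assumption, not a figure from the plan.

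**The case against.** The best defence is that the intent is evident. Every explicit alpha for the primary test is 0.025. For the performance endpoint, SAP 10 pairs a 95% interval with one-sided 0.025, which suggests the authors habitually meant the limit of a two-sided 95% interval and used "one-sided" for the bound they would read. Both conditions in SAP 11.6 are also worded as requirements, so one could argue that both must hold, the stricter governs, and 7/75 fails. The sample-size report in CIP Appendix F, which is not among the documents available, may state the rule.

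The point about intent stands: 0.025 is very probably what was meant, and the SAP never writes 0.05 for the primary endpoint. It does not remove the conflict. The closing sentence of SAP 11.6 ties rejection to a 95% interval of unstated sidedness, and the sample-size text expressly endorses a one-sided interval, so the literal reading remains open. An appendix would not correct the SAP's own criterion.

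Two qualifications on size also stand. The ITT safety set keeps enrolled subjects through their last follow-up, so its denominator should stay near 75 or above; 67–73 matters mainly for the per-protocol set. And if the device performs at 5%, the disputed count is uncommon.

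**Conclusion.** The concern holds. As written, SAP 11.6 contains a 0.05 rule and a 0.025 rule for the same primary hypothesis. At 75 subjects the literal interval rule has an exact type I error of 4.6%, above the stated 2.5%; the 0.025 rule has 2.0% with 91.9% power at a true 5% rate. The practical difference is one event at most sample sizes near the target, and at 75 subjects that event is the seventh.

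These figures assume the limit of 0.17, exact binomial calculation, independent subjects and a per-subject count. The conflict of levels would remain if closures were the unit; the disputed counts would follow the number of closures. This must be fixed before analysis because it decides the study's only primary claim.

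**What to change.** In the claim criterion of SAP 11.6, replace the one-sided 95% interval with a one-sided 97.5% exact (Clopper–Pearson) upper bound, and say that this is the upper limit of the two-sided 95% interval. In the closing sentence of the section, specify a two-sided 95% interval. Add the 97.5% level where SAP 10 refers to a one-sided interval. State that the passing count follows from the number actually analysed, for example at most 5 events for 67–73 subjects and at most 6 for 74–80.

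Two minor clarifications fit the same revision: say that the performance interval in SAP 10 and 11.7 is two-sided 95%, and say in SAP 11.2 that the optional interim analysis carries no success claim.

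The cost is SAP wording. The planned 75 need not change. Against the literal interval rule, the corrected rule is stricter by at most one event for 60–90 subjects. The revision should disclose that exact power under the 0.025 rule is 91.9% at 75 but 87.6% at 68, and between 84% and 88% across 67–73, below the stated 90%.

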11.7 Secondary endpoints

Two secondary endpoints will be summarised for the entire group of subjects/closures:

-Minor device related vascular access site complications per subject up to 1 months (safety endpoint)

-Technical success rate for the PerQseal® closure device at discharge per closure is no worse than the technical success rates associated with the 'perclose' or 'preclose' technique following EVAR or TAVR.

The criteria for successful performance of the investigational device have been aligned with what is reported within the literature, ensuring a like for like comparison. A literature based performance control is the only effective source of data available for this study, as it is not applicable to compare the performance of a device with that of a surgical technique of cut-down and sutured closure, used for the safety control. Therefore, the performance of the PerQseal® (i.e. the proportion of successful closures) will be assessed by comparison of the proportion of PerQseal® closures which achieve acute haemostasis at the arteriotomy site and do not lead to alternative treatment (other than manual compression or adjunctive endovascular ballooning) (Pperformance) from the mITT group against a performance goal for performance (PGperformance). This will be achieved by testing for non-inferiority against a performance non-inferiority limit (NLP), which is the predetermined PGperformance minus a non-inferiority margin delta. In order to claim non-inferiority against a performance driven PGperformance the lower bound of a (95%) confidence interval for the proportion of successful "Pperformance" (using the exact method for estimating a Binomial proportion) must be shown to be greater than the non-inferiority limit.

The PG_{performance} and non-inferiority margin delta have been derived from a Meta-analysis of performance rates for percutaneous device closure (Prostar® XL and Perclose ProGlide®) from comparable patient populations reported in the literature.

The proportion with successful closure is estimated to be 0.84 with a 95% Confidence Interval of 0.81 to 0.87. Given that the lower bound is 0.81 this justifies the use of 0.84 as valid $PG_{performance}$ minus a non-inferiority margin of 0.03 yielding an overall non-inferiority limit (N_{LP}) of 0.81 for performance.

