- x. Females who are pregnant or lactating or in fertile period not taking adequate contraceptives. A pregnancy test may be performed.
- xi. Patients that have a lower extremity amputation from the ipsilateral or contralateral limb.

Procedural Exclusion Criteria*:

- xii. Arterial access other than common femoral artery obtained for ipsilateral target leg.
- xiii. Subject has a tissue tract expected to be greater than 10 cm.
- xiv. Use of thrombolytic agents within 24 hours prior to or during the endovascular procedure which causes fibrinogen < 100 mg/dl.
- xv. Significant blood loss/transfusion (defined as requiring transfusion of 4 or more units of blood products) during index procedure or within 30 days prior to index procedure.
- xvi. Activated clotting time (ACT) > 350 seconds immediately prior to sheath removal or if ACT measurements are expected to be > 350 seconds for more than 24 hours after index procedure.
- xvii. Target puncture site is located in a vascular graft.
- xviii. Target arteriotomy in the profunda femoris or superficial femoral artery or is in common femoral artery, but within 10 mm proximal of the bifurcation of the Superficial Femoral /Profunda Femoris artery.
- xix. PerQseal® Introducer-sheath to ipsilateral femoral artery diameter ratio is greater than or equal to 1.05. (For S Introducer vessel lumen diameter of less than 6 mm. For L Introducer vessel lumen diameter of less than 7 mm.)

xx. Subjects with an acute haematoma of any size, arteriovenous fistula or pseudoaneurysm at the target access site; or angiographic evidence of arterial laceration or dissection within the external iliac or femoral artery before the use of the PerQseal® closure device.

*May not be known until after the patient has given informed consent and the procedure has started. In this event, the PerQseal® should not be used and the patient should be considered excluded from the study and intention to treat analysis. Note: The use of a secondary closure device in the same leg is prohibited during this study. A note to this effect should be entered into the patient's medical records.

Risks

The following risks are the anticipated potential vascular complications associated with use of the PerQseal® closure device:

- Haematoma.
- Bleeding.
- Dissection
- Pseudoaneurysm.
- Stenosis at the closure site.
- Arteriovenous fistula.

Other events that could possibly occur include:

- Retroperitoneal bleeding.

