- Bleeding causing hypovolemic shock or severe hypotension requiring vasopressors or surgery (BARC type 3b) OR
- Overt source of bleeding with drop in haemoglobin of ≥5 g/dL or whole blood or packed red blood cells (RBCs) transfusion ≥4 units* (BARC type 3b)

Major bleeding (BARC type 3a)

- Overt bleeding plus haemoglobin drop of 3 to <5 g/dL (provided haemoglobin drop is related to bleed); AND
- Does not meet criteria of life-threatening or disabling bleeding.

Minor bleeding (BARC type 2 or 3a, depending on the severity)

• Any bleeding worthy of clinical mention (e.g. access site haematoma) that does not qualify as life-threatening, disabling, or major bleeding.

Technical Success Rate – Technical Success Rate (TSR) is defined as the number of PerQseal® closure devices that are deployed and achieve haemostasis (i.e. cessation of bleeding (excluding cutaneous or subcutaneous oozing)), without need for any alternative treatment (other than manual compression or adjunctive endovascular ballooning) at target access site, divided by the total number of PerQseal® devices where deployment was attempted (as per the PerQseal® closure device IFU). Device malfunction resulting in alternative therapy will be considered as a technical failure.

REVISION	DCN				
AA	2772				
AB	2966				

² Kappetein AP, Head SJ, Généreux P, et al. Updated standardized endpoint definitions for transcatheter aortic valve implantation: the Valve Academic Research Consortium-2 consensus document. *European Journal of Cardio-Thoracic Surgery* 42 (2012) S45–S60.

^{*}Adapted from VARC-22.

^{*}Given one unit of packed RBCs typically will raise haemoglobin concentration by 1 g/dL, an estimated decrease in haemoglobin will be calculated.

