- ix. **Time to Haemostasis** Time to haemostasis (TTH) is determined as the elapsed time from when the Introducer-sheath and PerQseal® closure device have been removed from the patient to first observed cessation of bleeding (excluding cutaneous or subcutaneous oozing) at the target access site arteriotomy.
- x. **Time to Ambulation** Time to Ambulation (TTA) is defined as the time from post procedure sheath removal until the patient is comfortable walking approximately 6 m.
- xi. **Time to Device Deployment** Time to Device Deployment (TTDD) is defined as the time from insertion of the PerQseal[®] closure device into the Introducer-sheath to complete removal of the PerQseal[®] closure device and Introducer-sheath from the patient following deployment.
- xii. **Overall Procedural Time** Overall Procedural Time (OPT) is defined as the time from first invasive contact with the patient's groin to completion of all aseptic procedures related to the groin.
- xiii. **Technical Success Rate** Technical Success Rate (TSR) is defined as the number of PerQseal® closure devices that are deployed and achieve haemostasis (i.e. cessation of bleeding (excluding cutaneous or subcutaneous oozing)) without need for any alternative treatment (other than manual compression or adjunctive endovascular ballooning) at target access site, divided by the total number of PerQseal® closure devices where deployment was attempted (as per the PerQseal® closure device IFU). Device malfunction resulting in alternative therapy will be considered as a technical failure.
- xiv. **Surgical Closure** Standard surgical vascular access and sutured closure.
- xv. **Baseline** Prior to interventional procedure.
- xvi. **Endovascular Aortic/Aneurysm Repair (EVAR)** Endovascular surgery used to treat an abdominal aortic aneurysm (AAA).
- xvii. **Thoracic Endovascular Aortic/Aneurysm Repair (TEVAR)** Endovascular surgery used to treat a Thoracic aortic aneurysm.
- xviii. **Transcatheter Aortic Valve Replacement (TAVR)** Procedure in which a bioprosthetic valve is inserted through a catheter and implanted within the diseased native aortic valve. Also known

as Transcatheter Aortic Valve Implantation (TAVI) or Percutaneous Aortic Valve Replacement (PAVR).

- xix. **Activated Clotting Time (ACT)** Measures the intrinsic clotting activity of whole blood in seconds.

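### The plan's counting rules for technical success conflict, so a device-caused non-deployment controlled by compression or ballooning alone can be a failure, a success or an exclusion

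*SAP*

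**What the plan says.** Five places in the SAP bear on how technical success is counted.

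- **SAP 4.2 xiii**, matching the protocol's Definitions. The numerator is "defined as the number of PerQseal® closure devices that are deployed and achieve haemostasis" with no alternative treatment beyond manual compression or ballooning. The denominator is "divided by the total number of PerQseal® closure devices where deployment was attempted (as per the PerQseal® closure device IFU". A further sentence adds: "Device malfunction resulting in alternative therapy will be considered as a technical failure".
- **SAP 11.7**, which sets up the test. The endpoint is introduced as "Technical success rate for the PerQseal® closure device at discharge per closure is no worse than" the literature rate. The tested proportion is then described as "closures which achieve acute haemostasis at the arteriotomy site and do not lead to alternative treatment (other than manual compression or adjunctive endovascular ballooning", taken from the mITT group. Deployment is not mentioned.
- **SAP 11.1** builds the mITT set from all closures in enrolled subjects with an attempted closure. It leaves out devices prevented from deploying by an exclusion criterion or by the primary procedure.
- **SAP 9.3.1** takes out of the performance analysis every exposed patient whose device was not deployed for any reason other than device failure. **SAP 4.2 viii** defines device failure as a failure that results in interventional or surgical correction.
- **SAP 11.10** says that implanted subjects will be assessed for technical success.

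The protocol's note to the procedural exclusion criteria adds: "The use of a secondary closure device in the same leg is prohibited during this study". The SAP's copy of that footnote (9.3.3) does not carry the sentence. Table 4 shows technical success only as a percentage with n/N. Table 13 lists device malfunctions, but not non-deployments or the number of devices used per limb.

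**The concern.** A tested endpoint needs one numerator, one denominator and one unit. Here the definition requires deployment and the test does not, and three other sections set the denominator in different ways. No section is given precedence.

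The performance claim is a comparison with a fixed literature limit in an unblinded, single-arm study. The success rule therefore has a direct effect on the result, and someone who knows the outcomes could choose between the readings after the fact. The 11.7 wording can also credit the device with haemostasis that compression produced. The planned tables would not let a reader see which rule had been used.

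**Working it through.** **Inputs.** Limit 0.81, that is 0.84 minus 0.03 (SAP 11.7). One-sided level 0.025 (SAP 10). Exact binomial method (SAP 11.7). Planned size 75 treated subjects (SAP 10). I assume 75 closures; bilateral cases would raise the number.

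**The plan's own figure.** SAP 10 gives 44 closures for 90% power but does not state the expected success rate, so 44 can only be solved backwards. With n = 44 the test needs at least 41 successes: P(X ≥ 41 | 44, 0.81) = 0.022. Power reaches 0.90 if the true rate is about 0.96. The figure is plausible but cannot be reproduced independently, and it does not show which success rule was in mind.

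**One limb through each set of rules.** The PerQseal is attempted, does not deploy for a device reason, and manual compression or ballooning alone controls the bleeding.

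| Rules applied | Reasoning | Result |
|---|---|---|
| 4.2 xiii and the protocol | Attempted, so in the denominator; not deployed, so not in the numerator | Failure |
| 11.1 with 11.7 | Not stopped by an exclusion criterion or the primary procedure, so stays in mITT; haemostasis without disallowed treatment | Success |
| 9.3.1 with 4.2 viii | No interventional or surgical correction, so not a device failure; non-deployment for another reason | Excluded |
| 11.10, if read as the denominator | Not implanted | Excluded |

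The malfunction sentence in 4.2 xiii does not settle the case. It adds one route to failure and does not waive the deployment condition.

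**Effect at the boundary.** The exact lower bound L for x successes in n solves P(X ≥ x | n, L) = 0.025, which is the 0.025 quantile of Beta(x, n − x + 1). The claim is met if L > 0.81. With 75 closures the minimum is 68 successes, and P(X ≥ 68 | 75, 0.81) = 0.0175. Let 67 other limbs be clear successes, 7 clear failures, and one limb be as above.

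- Counted as success: 68/75 = 0.907, L = 0.8171, passes.
- Counted as failure: 67/75 = 0.893, L = 0.8006, fails.
- Excluded: 67/74 = 0.905, L = 0.8148, passes.

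**How often the boundary arises.** P(X = 68) = C(75,68) p^68 (1 − p)^7. This is 0.020 at p = 0.96, 0.005 at 0.97, 0.154 at 0.90 and 0.038 at 0.84. These rates are assumptions.

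**Error rate.** Suppose the true rate under 4.2 xiii is exactly 0.81 and the 11.7 wording turns a further 1, 2 or 3 percentage points of attempts into successes (assumed; the documents give no non-deployment rate). Then P(X ≥ 68 | 75) at 0.82, 0.83 and 0.84 is 0.029, 0.046 and 0.072. The nominal level is 0.025.

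**A second PerQseal in one limb.** If this occurred and did not count as alternative treatment, 68 closed limbs would be 68/75 per closure (0.8171, passes) but 68/76 per device (0.8031, fails). Both conditions are uncertain; see the objection.

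**The case against.** **The rules may already exclude the limb.** Read literally, 9.3.1 with 4.2 viii takes it out of the performance analysis, which gives 67/74 and a pass. That is a fair reading, but 11.1 defines the analysis set for this endpoint and does not remove the limb. The objection supplies one of the three answers and gives no reason to prefer it.

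**11.7 may only paraphrase.** It uses the defined term, and a limb closed by compression is arguably not a PerQseal closure at all. This is a natural reading. But 11.7 then writes out its own criterion, without deployment, as the quantity to be tested, and does not refer back to 4.2.

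**Two stronger inferences are tempting and do not hold.**

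- A reader might infer that abandoned attempts in general become successes in the test. They do not. Attempts stopped by exclusion criteria or the primary procedure leave the mITT set under 11.1, and 9.3.1 removes more. Attempts that end in surgery or a stent-graft fail under both wordings.
- A reader might infer that replacing a failed PerQseal with another is an established route to an inflated rate. The protocol note appears to prohibit it. If a second PerQseal is alternative treatment, the limb fails under both wordings. What stands is that the note does not say whether it covers a second PerQseal, the SAP omits it, and neither document says how such a deviation is counted.

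Counting per limb is likewise not a departure by the SAP. The protocol's Study Design already treats each limb as a separate closure, and with one device per limb the two units coincide.

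**Size and comparability.** The endpoint is secondary and does not drive the sample size, and the change of conclusion needs a result at the boundary. Both points stand and limit the weight of the concern. It is also fair that a stricter study criterion, such as crediting only the first device used, appears in neither document and could disturb the like-for-like comparison that 11.7 claims with the literature.

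**Conclusion.** The plan contradicts itself on a tested endpoint. The contradiction has a clear effect in one situation: a device-caused non-deployment managed by compression or ballooning alone. The rules then give failure, success or exclusion. At an assumed 75 closures, one such limb at the boundary decides between a lower bound of 0.801 (fails) and 0.817 or 0.815 (passes). Away from the boundary a single limb changes nothing, and the documents give no rate for such cases, so the likely effect on the claim cannot be estimated from them. The full investigation plan and the instructions for use, which 4.2 xiii relies on to define an attempt, were not available and might narrow the gap. This should be corrected, but it does not threaten the primary endpoint or the sample size.

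**What to change.** 1. Make 4.2 xiii govern the test: add the deployment condition to the 11.7 success criterion and apply it per limb.
2. Align 9.3.1, 11.1, 11.10 and Table 4. Every attempted limb stays in the denominator unless non-deployment was due to an exclusion criterion or the primary procedure. A device-caused non-deployment counts as a failure however haemostasis was then obtained.
3. Report in Table 13 the number of non-deployed devices and the number of devices used per limb.
4. Reconcile the protocol note on a secondary closure device with the SAP footnote that omits it, and state in the SAP how a limb with a second PerQseal is counted if one occurs as a deviation.

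The cost is wording, mainly in the SAP, plus whatever the reconciliation in item 4 requires in the protocol. Enrolment and sample size do not change. The technical success rate may come out slightly lower. The sponsor should also confirm that the criterion still matches the definition used in the literature behind 0.84 and 0.81.
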